3.5 Safety Analyses

All safety analyses will use the Safety Set unless otherwise specified. Unless noted otherwise, denominators for all tables will be number of patients in the SS. For visit based safety endpoints including laboratory assessments, vital signs, and ECG, the analyses will use nominal visit collected by CRF. Early termination visit will be treated as Week 25/Week 27 for summary table.

Most AE summary tables, lab shift and abnormality tables will be based on two sets of data: on-treatment and on-study. On-treatment period is from the first dose through one dosing interval post last dose. For cohort A (weekly dose), on-treatment period spans time from first dose to the last dose

+ 7 days; For cohort B&C (every 4-week dose), on-treatment period spans time from first dose to the last dose + 28 days. On-study period is from the first dose until the patient's last contact date within the study.

Safety endpoints include the following:

- Adverse events
- Clinical safety laboratory tests
- Vital signs
- ECG

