3.5.1 Adverse Events

All adverse events will be coded by the MedDRA dictionary version 20.1. Missing or partial dates will be imputed as outlined as below under conservative principles:

Missing or partial start dates:

If year, month and day are all missing then assign the date of first administration of Study Drug

- If month and day are missing and year is:
 - the same as the year of the first administration of Study Drug then assign the month-day of first Study Drug
 - earlier than the year of the first administration of Study Drug then assign December 31
 - after the year of the first administration of Study Drug then assign January 1
- If only day is missing and month-year is:
 - the same as the month-year of the first administration of Study Drug then assign the day of first Study Drug
 - earlier than the month-year of the first administration of Study Drug then assign the last day of the month
 - after the month-year of the first administration of Study Drug then assign the first day of the month

Imputation will be performed for the end date only if the day or month is missing (i.e., year is present) for a resolved AE as follows:

- If month and day are missing and year is:
 - the same as the year of the last dose of Study Drug then assign the month-day of the last dose of Study Drug
 - otherwise, assign December 31
- If only day is missing then assign the last day of the month

If the imputed start date is later than the imputed end date then set the imputed start date to the imputed end date.

AE summary tables will be based on two sets of data: on-treatment period and on-study period defined in section 3.5. Imputed AE start date and end date will be used to determine whether AE is on-treatment or on-study. On-treatment AE summary tables include all AEs with imputed start date or

imputed end date fall in on-treatment period. On-study AE summary tables include all AEs with imputed start date or imputed end date after first dose date.

Treatment-emergent adverse events (TEAEs) are defined as adverse events that occurred after the first administration of Study Drug. An AE with a completely missing start date will be assumed to be treatment emergent. If the onset date/time is the same as or after the date/time of the first administration of Study Drug, then the event is considered to be treatment emergent. Note that imputed dates will be used for defining TEAEs.

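### The SAP 3.5.1 selection rule for on-study AE tables uses a strict boundary, so TEAEs dated to the first-dose day that end that day, or have no end date, can be missing from those tables while staying in the on-treatment tables

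*SAP*

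**What the plan says.** SAP 3.5 (Safety Analyses) defines two reporting periods that both begin at the first dose: "On-treatment period is from the first dose through one dosing interval post last dose", and "On-study period is from the first dose until the patient's last contact date within the study".

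SAP 3.5.1 (Adverse Events) ties the tables to those definitions: "AE summary tables will be based on two sets of data: on-treatment period and on-study period defined in section 3.5". It then gives a selection rule for each set. The on-treatment rule takes AEs whose imputed start or end date lies in the on-treatment period. The on-study rule is worded differently: "On-study AE summary tables include all AEs with imputed start date or imputed end date after first dose date".

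Three other rules in 3.5.1 matter here:

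- The test for a treatment-emergent AE (TEAE) is inclusive: "If the onset date/time is the same as or after the date/time of the first administration of Study Drug", the event counts.
- Incomplete start dates are often placed on the first-dose day. For a fully missing date: "If year, month and day are all missing then assign the date of first administration of Study Drug". When only the day is missing and the month and year are "the same as the month-year of the first administration of Study Drug then assign the day of first Study Drug". A start date with only the year known, matching the first-dose year, is treated the same way.
- End dates are imputed only for resolved AEs with a known end year. An ongoing AE, or one whose end year is missing, has no end date.

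SAP 3.5.1.1 counts an injection-day event with no resolution date as an injection site reaction (ISR). It reports the percentage of injections leading to an ISR, ISRs by injection location, and incidence and time to first ISR for the on-study period only.

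**The concern.** The on-study period runs from the first dose to last contact, so it should contain the whole on-treatment period. Any AE in an on-treatment table should therefore be in the matching on-study table. The selection sentence breaks this at one point, the first-dose date: the period includes that date and the table rule does not. A programmer who codes the sentence as written will use a strict inequality.

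This date matters because the SAP's imputation, described there as conservative, places AEs of unknown onset on it, and because reactions to the first injection occur on it. An on-study table with fewer patients for a term than its on-treatment counterpart would be visibly inconsistent in the study report. For the ISR summaries produced on-study only, there is no on-treatment table to show the omission.

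**Working it through.** The SAP states no figure on this point, so there is none to reproduce. The check applies the written rules to each possible date pattern.

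Let F be the first-dose date, S the imputed start date, E the imputed end date (possibly absent), and T the end of the on-treatment period (last dose plus 7 days in Cohort A, plus 28 days in Cohorts B and C, from SAP 3.5).

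- TEAE (3.5.1): S ≥ F, using time of onset where recorded.
- On-treatment table: F ≤ S ≤ T, or F ≤ E ≤ T.
- On-study table as written: S > F, or E > F.
- On-study table with an inclusive boundary: S ≥ F, or E ≥ F.

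An absent E is taken as failing a test on E. That is an assumption, since the SAP is silent. Day 1 onsets are taken as not before the dose.

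| AE pattern | TEAE | On-treatment | On-study as written | On-study inclusive |
|---|---|---|---|---|
| S = F, E = F | yes | yes | **no** | yes |
| S = F, E = F + 1 day | yes | yes | yes | yes |
| S = F, E = F + 2 days (shortest first-injection ISR with a recorded resolution) | yes | yes | yes | yes |
| S = F, ongoing | yes | yes | **no** | yes |
| Day of onset missing in the first-dose month (S set to F), ongoing | yes | yes | **no** | yes |
| Onset fully missing (S set to F), end year missing | yes | yes | **no** | yes |
| Day of onset missing (S set to F), end day imputed to a later month end | yes | yes | yes | yes |
| Onset fully missing (S set to F), year-only end imputed to a later last dose | yes | yes | yes | yes |
| S = F + 1 day, ongoing | yes | yes | yes | yes |
| S before F, E after F | no | yes | yes | yes |

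The literal and inclusive rules differ only where S = F and E is either F or absent. The first row needs no assumption about missing end dates. The other three exclusions do.

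The last row shows what the separate TEAE filter does: an AE with onset before dosing is selected by both on-study rules through its end date, and the TEAE filter then keeps it out of the TEAE tables.

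For ISRs, 3.5.1.1 requires a recorded resolution date to be neither the injection day nor the day after. For the first injection this means E ≥ F + 2, so the event passes through its end date. With no resolution date, the event still counts as an ISR but fails the literal on-study rule. This reaches the on-study-only ISR summaries if the 3.5.1 sentence governs them, which the SAP does not state separately.

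On size: SAP 3.2.5 plans about 24 patients per group, so one patient is 1/24 = 4.2 percentage points. SAP 3.5.1 lists as most common those preferred terms with incidence of 10% or more in any group. Three patients give 3/24 = 12.5% and two give 2/24 = 8.3%. One lost patient can therefore take a term off the on-study list if no other group reaches 10%.

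**The case against.** The strongest reply is that this is loose drafting. Section 3.5.1 points to the periods in 3.5, which include the first-dose day. Its TEAE definition also begins by speaking of events after the first administration and then explains that this means the same time or later. A programmer reading the sections together might well include Day 1. That is possible, but the on-study sentence has no such explanation and is written at date level. The intent is probably inclusive; the rule as written is not.

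The second reply concerns ongoing AEs. Nothing in the SAP says that a missing end date fails the test, and an AE still ongoing after Day 1 plainly ends later. Elsewhere the SAP keeps such records: a medication started before the first dose with a missing stop date counts as concomitant (3.2.7), and injection-day events with no resolution date count as ISRs (3.5.1.1). This stands in part. For these AEs, 3.5.1 is silent and loses events only under one reading.

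A reader might go further and infer that all first-dose-day AEs, or acute reactions to the first injection generally, vanish from the on-study tables. The documents do not support that. The rule accepts a start date or an end date, so an AE ending on a later day stays in. First-injection ISRs with a recorded resolution date always stay in. Local cutaneous reactions are summarized on-treatment only, and the flu-like reaction summaries by definition are presented on-treatment (3.5.1.1, 3.5.1.2). Nor is every Day 1 AE treatment-emergent: AE recording starts at consent (Protocol 9.4.2), and one with a recorded onset time before the dose is not a TEAE.

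It is also true that the on-treatment tables keep the affected events and the listings show all recorded data (SAP 3.2.1). No event disappears from the report as a whole.

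**Conclusion.** The point holds in a limited form. As written, the on-study rule contradicts the period it is meant to apply. A TEAE that starts on, or is imputed to, the first-dose date and resolves on that date is in the on-treatment tables and missing from the on-study tables. This follows from the text alone.

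TEAEs dated to that day with no end date are missing too, on the assumption that an absent end date is not treated as later. These include first-injection ISRs without a resolution date, some of whose summaries exist only on-study.

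The documents give no rate of Day 1 AEs or of missing end dates, so the number affected cannot be derived and no estimate is offered. A patient leaves the any-AE count only if no other AE of that patient qualifies, so the effect is more likely in single preferred terms than in overall incidence. The primary and secondary efficacy analyses are not touched. This is a defect of wording that should be corrected; it does not show that events have been or will be lost.

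**What to change.** Reword the on-study selection sentence in SAP 3.5.1 along these lines: *an AE is selected for the on-study tables if its imputed start or end date falls on or after the date of first dose and no later than the last contact date; an AE without an end date is regarded as continuing to last contact.*

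Keep both the start-date and the end-date routes. Dropping the end-date route would change which AEs with onset before dosing are selected in any output that is not limited to TEAEs. Keep the existing TEAE filter, with time of onset used on Day 1 where recorded, so that events before the dose stay out of the TEAE tables. State that the same rule governs the on-study ISR summaries in 3.5.1.1.

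Add one programming check: every TEAE in the on-treatment set must also be in the on-study set.

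The cost is one revised sentence, one cross-reference and one check. No data collection, imputation rule or clinical procedure changes.

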3.5.1.1 Treatment Emergent Adverse Events at Injection Site

Treatment-emergent AEs at injection site will follow two definitions:

Definition 1: Local cutaneous reactions at injection site (LCRIS) are defined as any AE with PT containing injection site erythema, injection site swelling, injection site pruritus, injection site pain, or injection site tenderness that started on the day of injection and persisted for at least two days (i.e. event onset date on the day of injection and resolution date not on the day of injection or the day after injection). Events on the day of the injection with a missing resolution date are also included.

Definition 2: Injection Site Reactions (ISR) defined as any AE with PT or verbatim term containing 'Injection Site' that started on the day of injection and persisted for at least two days (i.e. event onset date on the day of injection and resolution date not on the day of injection or the day after injection). Events on the day of the injection with a missing resolution date will also be included.

Treatment-emergent LCRIS will be summarized by SOC and PT and by severity on-treatment only. Treatment-emergent ISRs will be summarized by SOC and PT and by severity in on-treatment and on-study periods.

Additionally, the following will be summarized using Definition 2 (i.e., ISRs) for on-study period only:

- Percentage of injections leading to ISR for overall and preferred term will be summarized using descriptive statistics. Percentage of injections leading to ISR will be calculated as follows for each patient: $(A/B) * 100$, where A = number of injections leading to ISR, and B = total number of injections.
- ISRs by injection location
- Incidence of ISR and time to first ISR

An additional table summarizing ISRs (Definition 2) on-treatment by SOC and PT and by severity within cohort will be presented.

3.5.1.2 Treatment Emergent Flu-Like Reactions (FLR)

Treatment Emergent Flu-Like Reactions (FLRs) will follow two definitions:

- **Definition 1:** TEAEs with either (i) influenza like illness or (ii) at least one of following PTs: pyrexia, feeling hot, or body temperature increased, plus at least two of the following PTs: chills, myalgia, and arthralgia, starting on the day of injection or the next day.
- **Definition 2:** TEAEs with following PTs or verbatim: influenza like illness, chills, myalgia, arthralgia, pyrexia, feeling hot, or body temperature increased, starting on the day of injection or the next day.

Note that imputed dates may be used for defining FLRs.

Treatment Emergent FLRs defined in Definition 1 will be summarized by category (i) or (ii). Treatment Emergent FLRs defined in Definition 2 will be summarized by SOC and PT. Both definitions will be presented for on-treatment.

Percentage of injections leading to FLRs (Definition 2) for overall and by preferred term will also be summarized using descriptive statistics. Percentage of injections leading to FLRs will be calculated for each patient as $(A/B)*100$, where A is the number of injections associated with FLRs, and B is the total number of injections.

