### **3.3 Number of Subjects**

Approximately 96 subjects are planned to be enrolled in this study.

Approximately 32 subjects will be assigned to each cohort, with 24 subjects receiving ISIS 703802 and 8 receiving placebo.

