1.1 Study Overview

Protocol ISIS 703802-CS2 is a Phase 2 multicenter, randomized, double-blind, placebo-controlled, dose-ranging study being conducted in the United States and Canada. After screening, up to 96 eligible patients randomized to 1 of the 3 dosing cohorts. Each cohort has a 3:1 ratio to receive ISIS 703802 or matching volume of placebo by SC injection as below.

Cohort A (20 mg QW, n = 32): 20 mg ISIS 703802 or placebo (3:1) once every week for 26 doses.

Cohort B (40 mg Q4W, n = 32): 40 mg ISIS 703802 or placebo (3:1) once every 4 weeks for 6 doses.

Cohort C (80 mg Q4W, n = 32): 80 mg ISIS 703802 or placebo (3:1) once every 4 weeks for 6 doses.

Following End-of-Treatment (EoT) assessments, all patients will then enter a 13-week post-treatment follow-up period.

The primary safety and efficacy analysis time point is at Week 27 for patients who received weekly dosing and at Week 25 for patients who received every 4-week dosing.

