3 ANALYSIS PLAN

3.1 Statistical Design Summary

This is a multi-center, randomized, double blind, placebo-controlled study.

The study hypotheses will be formally evaluated at the planned EoT analysis. The primary and secondary endpoints for the study will be recorded at Week 27 for Cohort A (ISIS 703802 and

Placebo) and Week 25 for Cohorts B and C (ISIS 703802 and Placebo) and where applicable may be based on analysis windowing rules found in Appendix A.

The treatment groups proposed in this analysis are defined as ISIS 703802 20 mg weekly (20 mg QW), ISIS 703802 40 mg every 4 weeks (40 mg Q4W), ISIS 703802 80 mg every 4 weeks (80 mg Q4W) and Pooled Placebo, defined as the combined group of placebo patients from the 3 randomized cohort groups.

EoT analyses will be conducted on data obtained through the data cut-off date, defined as the date of the last EoT visit. The database will be queried and data cleaning performed on all data, with database lock of all data, at which point the treatment code is unblinded and the EoT analyses are performed.

A final analysis will be performed after all data from the 13-week post treatment follow-up period are collected.

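### Minor: flu-like reactions count only around injections, so per-regimen incidence against a placebo group pooled over two schedules is not like for like; a same-schedule table would fix it

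*SAP*

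**What the plan says.** SAP 3.5.1.2 gives two FLR definitions. Definition 1 needs influenza-like illness, or a fever-type term plus at least two of chills, myalgia and arthralgia. Definition 2 accepts any one of those terms. Both require onset "starting on the day of injection or the next day". Definition 1 is tabulated by category and Definition 2 by system organ class and preferred term, and the SAP adds: "Both definitions will be presented for on-treatment". A per-patient percentage of injections leading to FLRs is also planned, for Definition 2 only.

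The schedules are in SAP 1.1:
- Cohort A: "20 mg ISIS 703802 or placebo (3:1) once every week for 26 doses"
- Cohort B: "40 mg ISIS 703802 or placebo (3:1) once every 4 weeks for 6 doses"
- Cohort C: "80 mg ISIS 703802 or placebo (3:1) once every 4 weeks for 6 doses"

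Protocol 3.3 gives each cohort about 32 subjects, "with 24 subjects receiving ISIS 703802 and 8 receiving placebo". SAP 3.1 names the treatment groups as the three active regimens and Pooled Placebo, "defined as the combined group of placebo patients from the 3 randomized cohort groups".

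For injection site reactions (ISRs), which are also tied to injection timing, SAP 3.5.1.1 plans a per-injection percentage and a further table: "An additional table summarizing ISRs (Definition 2) on-treatment by SOC and PT and by severity within cohort will be presented". SAP 3.5.1.3 plans a within-cohort table for bleeding too. FLRs have the per-injection percentage but no within-cohort table.

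**The concern.** Each injection opens a two-day window in which a symptom can qualify. A coincidental cold or aching joint therefore has more chances to count in a weekly injector than in a 4-weekly one, although both are on treatment for nearly the same time. Two thirds of pooled placebo inject every 4 weeks. The weekly column is then set against a comparator with about half its countable days, and each 4-weekly column against one with about twice its own.

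The Protocol Synopsis says safety and tolerability will be compared with placebo, and Protocol 2.4 treats 20 mg weekly and 80 mg every 4 weeks as giving equivalent exposure. A reader weighing those regimens could take the per-regimen FLR columns at face value. The weekly regimen would tend to look worse than placebo, and a true increase of up to about twofold in a 4-weekly arm could look like no increase.

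**Working it through.** **Group sizes.** The documents state no FLR incidence to reproduce. The figure that matters is the group size of about 24 in SAP 3.2.5. With 96 patients and 3:1 allocation, placebo is 96 × 1/4 = 24, or 8 per cohort. That is 8 weekly and 16 four-weekly, so 16/24 = 67% of pooled placebo inject every 4 weeks.

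**Countable days** (2 per injection):
- weekly: 26 × 2 = 52
- 4-weekly: 6 × 2 = 12
- pooled placebo mean: (8 × 52 + 16 × 12)/24 = 25.3, from a mean of (8 × 26 + 16 × 6)/24 = 12.7 injections

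**On-treatment time** (SAP 3.5; dosing days from Protocol Appendix A): 176 + 7 = 183 days weekly and 141 + 28 = 169 days 4-weekly. The imbalance comes from the counting window, not from length of follow-up.

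**Limiting ratios with no drug effect** (low background rate): weekly against pooled placebo 52/25.3 = 2.05; each 4-weekly arm 12/25.3 = 0.47.

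**Incidence.** Assume the same background rate r of qualifying symptoms in every arm. The documents give no value, so r is varied from 0.25 to 2 per patient-year. The chance of at least one counted FLR is 1 − exp(−r × countable days/365.25), and pooled placebo is (8 × weekly + 16 × 4-weekly)/24. At r = 1:
- weekly: 1 − exp(−52/365.25) = 13.3%
- 4-weekly: 1 − exp(−12/365.25) = 3.2%
- pooled placebo: (8 × 13.3 + 16 × 3.2)/24 = 6.6%

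| r per patient-year | Weekly | Each 4-weekly arm | Pooled placebo | Weekly / placebo | 4-weekly / placebo | Expected patients of 24 (weekly, 4-weekly, placebo) |
|---|---|---|---|---|---|---|
| 0.25 | 3.5% | 0.8% | 1.7% | 2.04 | 0.48 | 0.8, 0.2, 0.4 |
| 0.5 | 6.9% | 1.6% | 3.4% | 2.03 | 0.48 | 1.6, 0.4, 0.8 |
| 1 | 13.3% | 3.2% | 6.6% | 2.02 | 0.49 | 3.2, 0.8, 1.6 |
| 2 | 24.8% | 6.4% | 12.5% | 1.98 | 0.51 | 5.9, 1.5, 3.0 |

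**Robustness.** The weekly ratio is 1.95 at r = 3 and falls to 1.73 only at r = 10, when about 76% of weekly patients have an event. If 10% leave halfway through treatment it is 1.95 to 2.04 for r from 0.5 to 3. A fixed risk of 0.5% per injection gives 2.02. Onset dates imputed to the first dose fall in the window in every arm and would pull the ratio slightly towards 1.

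**What is not distorted.** The three active arms together average (52 + 12 + 12)/3 = 25.3 countable days, the same as pooled placebo, so that ratio is 1.00. In simulation at r = 1, the percentage of injections leading to FLRs averages 0.55% in both the weekly arm and pooled placebo. Comparing each active arm with placebo on its own schedule gives a ratio of 1.00 at every rate.

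**The case against.** Much of the case on the other side stands.

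- **A schedule-neutral measure is already planned.** It is limited to Definition 2, but every Definition 1 term is in the Definition 2 list with the same window, so Definition 1 events are included. It does not alter the incidence tables.
- **Tables without the window exist.** SAP 3.5.1 tabulates all treatment-emergent events by preferred term, so chills, myalgia, arthralgia and pyrexia also appear there over similar on-treatment time.
- **The comparator is inferred.** SAP 3.5.1.2 names no columns and the table shells are not available. Pooled placebo follows from the treatment groups in SAP 3.1 and from the absence of the within-cohort table given for ISRs and bleeding. SAP 3.5.1 also refers to a pooled active column, which is balanced.
- **The counts are small and the tables descriptive.** Over the assumed range the expected weekly excess over placebo is about 0.4 to 3 patients of 24, and no FLR test is planned.
- **The rates suit Definition 2.** Definition 1 is stricter, so its events would be fewer, although the ratio would be similar.

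A reader might infer that the weekly arm will show twice the placebo incidence, or that regimen choice will be biased. The documents support neither. The factor of two is an expectation under an assumed common rate, and chance variation at n = 24 could hide or exaggerate it. The Synopsis bases dose selection on triglyceride reduction, treatment-related serious events and other safety considerations such as platelet reductions; FLRs are not named. A reader might also want the same table for local cutaneous reactions at the injection site. Those reactions are a subset of ISRs under the same onset and persistence rule, and the planned within-cohort ISR table by preferred term and severity already shows them.

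**Conclusion.** The concern holds as a minor point of presentation. The per-regimen FLR incidence columns carry a predictable imbalance: about 2.0 times pooled placebo for the weekly arm and 0.5 times for each 4-weekly arm when the drug has no effect. The direction and approximate size follow from the injection counts and the pooling. They rest on three assumptions: background rates are equal across arms, they are not very high, and the tables use the SAP 3.1 groups. The absolute counts depend on a rate that the documents do not give.

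It would be wrong to infer that the FLR comparison with placebo is biased as a whole. The imbalance is confined to the per-regimen columns and threatens no formal inference. What remains is a gap in consistency: ISRs get both a per-injection summary and a within-cohort table, while FLRs get only the first.

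**What to change.** In SAP 3.5.1.2:

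1. Add an on-treatment FLR incidence table by dosing schedule, for both definitions. Set the weekly arm against Cohort A placebo (n = 8), and each 4-weekly arm against Cohort B and C placebo combined (n = 16).
2. Footnote the pooled FLR tables with the planned injection counts (26 against 6) and point to the per-injection summary.

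No extra table is needed for local cutaneous reactions.

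The cost is a small amount of programming on data already collected. The downside is small placebo groups. At one symptom per patient-year and no drug effect, the chance of no FLR at all is exp(−8 × 52/365.25) = 32% in Cohort A placebo and exp(−16 × 12/365.25) = 59% in the combined 4-weekly placebo. The pooled tables should therefore stay beside the new one.

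The new table does not repair the direct comparison of weekly with 4-weekly active arms, because those columns keep their 52 and 12 countable days. That comparison should rest on the percentage of injections leading to FLRs.
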